7.2.2 Inclusion criteria

The patients are included if they meet all the following criteria:

1. Patients with a new prescription date (index date) for tedizolid (ATC code: J01XX11) or linezolid (ATC code: J01XX08) during the cohort entry period (21-Aug-2018 to 31-Mar-2025).

A new prescription for tedizolid or linezolid is defined based on Tables 2 and 3.

Includes all patients who have been prescribed the above medications, regardless of whether they are outpatients, inpatients, or emergency cases.

2. Primary analysis: Patients with confirmed diagnosis of MRSA (ICD-10: A49.0 and disease name notation: MRSA infection) and confirmed diagnosis of indications for both tedizolid and linezolid (1: Deep Skin Infections, Chronic Abscesses, 2: Secondary infection of trauma, burns, and surgical wounds) in the same month or previous month of the index date. The disease code list is provided as Appendix A.

Sensitivity analysis-1 (see Section 7.8.3 (4)): Patients with confirmed or suspected diagnosis of MRSA (ICD-10: A49.0 and disease name notation: MRSA infection) and confirmed diagnosis of indications for both tedizolid and linezolid (1: Deep Skin Infections, Chronic Abscesses, 2: Secondary infection of trauma, burns, and surgical wounds) in the same month or previous month of the index date. The disease code list is provided as Appendix A.

Sensitivity analysis-2 (see Section 7.8.3 (5)): Patients with confirmed or suspected / probable diagnosis of MRSA (ICD-10: A49.0 and disease name notation: MRSA infection, Staphylococcal infection, MRCNS infection, MSSA infection, MRSE infection, and Vancomycin-resistant Staphylococcus aureus infection) and confirmed diagnosis of indications for both tedizolid and linezolid (1: Deep Skin Infections, Chronic Abscesses, 2: Secondary infection of trauma, burns, and surgical wounds) in the same month or previous month of the index date. The disease code list is provided as Appendix A.

Index date is the first prescription date of tedizolid or linezolid observed in the cohort entry period (21-Aug-2018 to 31-Mar-2025). That is defined by using the prescription order in the SS-MIX2 data of the MID-NET dataset. New tedizolid prescription patients will be tedizolid group and new linezolid prescription patients will be linezolid group.

Diagnosis of MRSA and indications for tedizolid or linezolid are defined by using the disease name order in the SS-MIX2 data or DPC data or Administrative claims data of the MID-NET dataset.

All age and sex will be included.

| | |
|--|--|
| PRODUCT: MK-1986 | PROTOCOL/AMENDMENT VERSION NO.: 1986-047-00-V3 |
| REVOPS ID NO: NIS106696 EPIDEMILOGY NO.(PE STUDIES ONLY): EP08063.004 | NIR DRC APPROVAL DATE: NOVEMBER 25, 2025 |

Table 2: The estimated treatment patterns in the tedizolid group

| Pre-treatment* | At index date | Inclusion/Exclusion |
|-----------------------|---------------------|---------------------|
| - | Tedizolid (J01XX11) | Inclusion |
| Linezolid (J01XX08) | Tedizolid (J01XX11) | Exclusion |
| Arbekacin (J01GB12) | Tedizolid (J01XX11) | Inclusion |
| Teicoplanin (J01XA02) | Tedizolid (J01XX11) | Inclusion |
| Daptomycin (J01XX09) | Tedizolid (J01XX11) | Inclusion |
| Vancomycin (J01XA01) | Tedizolid (J01XX11) | Inclusion |

* < 60 days before the index date [-60, -1]

Table 3: The estimated treatment patterns in the linezolid group

| Pre-treatment* | At index date | Inclusion/Exclusion |
|-----------------------|---------------------|---------------------|
| - | Linezolid (J01XX08) | Inclusion |
| Tedizolid (J01XX11) | Linezolid (J01XX08) | Exclusion |
| Arbekacin (J01GB12) | Linezolid (J01XX08) | Inclusion |
| Teicoplanin (J01XA02) | Linezolid (J01XX08) | Inclusion |
| Daptomycin (J01XX09) | Linezolid (J01XX08) | Inclusion |
| Vancomycin (J01XA01) | Linezolid (J01XX08) | Inclusion |

* < 60 days before the index date [-60, -1]

[figure not shown]
7.2.3 Exclusion criteria

Those with any of the following criteria will be excluded:

1. Patients who do not have 60 days lookback period prior to the index date.
To increase the number of patients included in the study, the lookback period was kept as short as possible. Based on the results of the feasibility study, changing the lookback period from 90 days to 30 days was estimated to increase the number of patients by approximately 10% (72.7% to 81.8% for tedizolid and 72.9% to 85.0% for linezolid, respectively). The analysis with a lookback period of 30 days will be performed as a sensitivity analysis (see Section 7.8.3 (2)).
2. Patients who have prescriptions for both tedizolid and linezolid on the same index date.
This exclusion criterion will exclude the patients who cannot be assigned to either of the exposure groups.
3. Patients who have one or more events of peripheral neuropathy and optic nerve disorder (see Section 7.3.2 for details) within 60 days lookback period.
The analysis with a lookback period of 365 days will be performed as a sensitivity analysis (see Section 7.8.3 (6)).
4. Patients who have prescription records for tedizolid or linezolid only on the index date.

| | |
|--|--|
| PRODUCT: MK-1986 | PROTOCOL/AMENDMENT VERSION NO.: 1986-047-00-V3 |
| REVOPS ID NO: NIS106696 EPIDEMILOGY NO.(PE STUDIES ONLY): EP08063.004 | NIR DRC APPROVAL DATE: NOVEMBER 25, 2025 |

Figure 1: Flow diagram

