7.2.4 Participant follow-up

The follow-up will begin on the day after the index date.

The follow-up end date will be defined as the date of treatment period end, date of death, the end of the study period, start date of other treatment drug, or date of outcome onset whichever comes first. The date of death means recorded in SS-MIX2 as “date of death” or “death” in the hospital visit information summary or recorded in the DPC file as “death” in the discharge summary. If discrepancies in the date of death are found between SS-MIX2 and DPC, preference is given to the DPC data. If the date of death is missing in the DPC data, the missing information will be supplemented using the SS-MIX2 data, if available.

[figure not shown]
Switching of the medication from one treatment group to another (from tedizolid to linezolid group or vice versa) or an addition of the other medication will also be considered as a termination of the initial treatment, and patients will be censored on the day of termination of the initial treatment, which will be operationally defined as the start of another treatment per

| | |
|---|--|
| PRODUCT: MK-1986 | PROTOCOL/AMENDMENT VERSION NO.: 1986-047-00-V3 |
| REVOPS ID NO: NIS106696 EPIDEMIOLOGY NO.(PE STUDIES ONLY): EP08063.004 | NIR DRC APPROVAL DATE: NOVEMBER 25, 2025 |

the database. Note, the additional date (date when another medication is added) and the switching date (overlapping treatment date) are included in the follow-up period.

Note, the previous feasibility study shows the median time to discontinuation of initial treatment as **CC1** days.

Figure 2: Follow-up Schema

a. the treatment period end, date of death, the end of study period, start date of other treatment drug, date of outcome onset, whichever comes first.

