7.3.2 Outcomes

The outcomes of interest in the study are peripheral neuropathy and optic nerve disorder.

Peripheral neuropathy is defined as cases meeting the following two conditions.

| | |
|---|--|
| PRODUCT: MK-1986 | PROTOCOL/AMENDMENT VERSION NO.: 1986-047-00-V3 |
| REVOPS ID NO: NIS106696 EPIDEMIOLOGY NO.(PE STUDIES ONLY): EP08063.004 | NIR DRC APPROVAL DATE: NOVEMBER 25, 2025 |

1. A confirmed diagnosis of peripheral neuropathy (ICD-10 code).
2. In the same month as, the month prior to, or the month after the confirmed diagnosis of peripheral neuropathy, a treatment drug for peripheral neuropathy or pain was prescribed, a test related to peripheral neuropathy was performed, or blood purification therapy for immune neuropathy was performed.

Optic nerve disorder is defined as cases meeting the following two conditions.

1. A confirmed diagnosis of optic nerve disorder (ICD-10 code).
2. In the same month as, the month prior to, or the month after the confirmed diagnosis of optic nerve disorder, vitamin B12 or corticosteroids were prescribed, or any of the relevant tests for optic nerve disorder (general, outpatient, or imaging tests) were performed.

The first event that meets any of the above definitions will be used for the analysis. The outcome occurrence date will be the earliest of the following: for Peripheral neuropathy, the prescription date of treatment drugs, the implementation date of blood purification therapy, or the test date; for Optic nerve disorder, the prescription date of treatment drugs or the test date.

Sensitivity analysis with variations of the about outcome definition regarding tests and treatment is detailed in Section 7.8.3 (7).

Although previous studies used ICD-9 codes to investigate peripheral neuropathy or ischemic optic neuropathy (7, 8), the codes identified in the literature might not be specific to the outcome in this study. Also, since there are no established diagnostic guidelines in Japan for peripheral neuropathy and optic nerve disorders, these definitions were established based on Japanese medical textbooks (9, 10) and Merck Manual Professional Version (11-15).

In addition, the above definition has been confirmed by medical doctor, and since there may be cases where tests and treatment drugs are not administered, an analysis using only diagnostic codes will be performed as a sensitivity analysis (see section 7.8.3 (8)).

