However, it is important to note that low number of patients with these dx codes in feasibility assessment (There was no 1st user of tedizolid had dx for peripheral neuropathy and optic nerve disorder in the 90-day lookback period).

[Data components used for capturing the outcome]

- Diagnosis will be captured using ICD-10 code or receipt code from diagnostic information (illness order) of SS-MIX2 or DPC diagnostic information of DPC data or receipt diagnostic information of administrative claims data.

| | |
|---|--|
| PRODUCT: MK-1986 | PROTOCOL/AMENDMENT VERSION NO.: 1986-047-00-V3 |
| REVOPS ID NO: NIS106696 EPIDEMIOLOGY NO.(PE STUDIES ONLY): EP08063.004 | NIR DRC APPROVAL DATE: NOVEMBER 25, 2025 |

- Prescription of therapeutic drugs will be captured using the ATC code or receipt code from prescription / injection order of SS-MIX2 or prescription / injection of SS-MIX2 or DPC drug information of DPC data or receipt drug information of administrative claims data.
- The test will be captured using the receipt code from DPC medical practice information of DPC data or receipt medical care information of administrative claims data.

The code list for outcome definition is in Appendix A.

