7.8.3 Sensitivity analyses

The following sensitivity analyses are planned:

- 1) The analysis will be conducted that does not allow for a history of administration of anti-MRSA drugs other than tedizolid and linezolid within lookback period.
- 2) The analysis will be conducted with the lookback period changed to 30 days.
- 3) The analysis will be conducted with the gap period changed to 7 days.
- 4) The analysis will be conducted with the following changes to the inclusion criteria 2.

Patients with confirmed or suspected diagnosis of MRSA (ICD-10: A49.0 and disease name notation: MRSA infection) and confirmed diagnosis of indications for both tedizolid and linezolid (1: Deep Skin Infections, Chronic Abscesses, 2: Secondary infection of trauma, burns, and surgical wounds) in the same month or

| | |
|---|--|
| PRODUCT: MK-1986 | PROTOCOL/AMENDMENT VERSION NO.: 1986-047-00-V3 |
| REVOPS ID NO: NIS106696 EPIDEMIOLOGY NO.(PE STUDIES ONLY): EP08063.004 | NIR DRC APPROVAL DATE: NOVEMBER 25, 2025 |

previous month of the index date. The disease code list is provided as Appendix A.

- 5) The analysis will be conducted with the following changes to the inclusion criteria 2. Patients with confirmed or suspected / probable diagnosis of MRSA (ICD-10: A49.0 and disease name notation: MRSA infection, Staphylococcal infection, MRCNS jinfection, MSSA infection, MRSE infection, and Vancomycin-resistant Staphylococcus aureus infection) and confirmed diagnosis of indications for both tedizolid and linezolid (1: Deep Skin Infections, Chronic Abscesses, 2: Secondary infection of trauma, burns, and surgical wounds) in the same month or previous month of the index date. The disease code list is provided as Appendix A.
- 6) The analysis will be conducted with the following changes to the exclusion criteria 3. Patients who have one or more histories of peripheral neuropathy and optic nerve disorder (see Section 7.3.2 for details) within 365 days prior to the index date.
- 7) The analysis will be conducted with the following changes to the outcome definition. Peripheral neuropathy is defined as cases meeting all of the following three conditions:
 1. A confirmed diagnosis of peripheral neuropathy (ICD-10 code).
 2. In the same month as, the month prior to, or the month after the confirmed diagnosis of peripheral neuropathy, either a treatment drug for peripheral neuropathy or pain was prescribed, or blood purification therapy for immune-mediated neuropathy was performed.

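### Prior neuropathy or optic nerve disease is screened out only if it already meets the two-condition case definition, so a coded prior diagnosis can be completed by a drug or test on treatment and counted as new

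*Protocol*

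**What the plan says.** Exclusion 3 in section 7.2.3 removes "Patients who have one or more events of peripheral neuropathy and optic nerve disorder (see Section 7.3.2 for details) within 60 days lookback period". For what an event is, it points to section 7.3.2.

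Section 7.3.2 sets two requirements: "Peripheral neuropathy is defined as cases meeting the following two conditions". The first is a confirmed ICD-10 code. The second is supporting care close in time: "In the same month as, the month prior to, or the month after the confirmed diagnosis of peripheral neuropathy, a treatment drug for peripheral neuropathy". Drugs for pain, related tests and blood purification also qualify. Optic nerve disorder is built the same way. The event is then dated by the supporting care and not by the diagnosis: "The outcome occurrence date will be the earliest of the following: for Peripheral neuropathy, the prescription date of treatment drugs", or the procedure or test date.

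The same section accepts that some diagnosed patients have no supporting care: "since there may be cases where tests and treatment drugs are not administered, an analysis using only diagnostic codes will be performed". That becomes sensitivity analysis 8.

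Sensitivity analysis 6 in section 7.8.3 lengthens the window but keeps the reference to section 7.3.2: "Patients who have one or more histories of peripheral neuropathy and optic nerve disorder (see Section 7.3.2 for details) within 365 days". Sensitivity analysis 8 makes the outcome code-only and dates it to the last day of the diagnosis month. It does not mention exclusion 3.

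On frequency, section 7.3.2 offers one statement from the feasibility work: "There was no 1st user of tedizolid had dx for peripheral neuropathy and optic nerve disorder in the 90-day lookback period". No linezolid count is given.

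**The concern.** A safety cohort needs a sensitive screen at entry, so that people who already have the condition are removed, and a more specific rule for counting events. Here the specific rule does both jobs. The patients it misses at entry are those section 7.3.2 acknowledges: coded, but without a drug or test.

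Such a patient carries half of the case definition into follow-up. One qualifying prescription, including a listed drug for pain, or one test on treatment supplies the other half. Old disease is then reported as a new event on the study drug. With very few true events expected in the tedizolid group, a single such patient matters for the reported rate.

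**Working it through.** **1. Does the route exist on the text?**

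- The screen looks for a section 7.3.2 event in the 60 days before the index date ([-60, -1] in Tables 2 and 3). A code alone is not an event, and no other criterion in 7.2.2 or 7.2.3 removes that patient.
- Section 7.3.2 does not require the diagnosis to be new or to follow the index date.
- The supporting drug or test may fall in the month after the diagnosis.
- The event takes the date of the drug or test, and "The follow-up will begin on the day after the index date".

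Illustration: index date 10 June, so the lookback runs from 11 April to 9 June. A neuropathy code is recorded on 20 May, with no qualifying drug, test or procedure up to 9 June. The patient is not excluded. A first nerve test on 18 June, while on treatment, falls in the month after the diagnosis. Both conditions are met, the event is dated 18 June, and it counts. The code need not be recorded again. A patient with a qualifying drug or test already dated in the lookback is correctly excluded.

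**2. Expected true events in the tedizolid group**

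Inputs from section 7.5: 8/662 = 1.2% (peripheral neuropathy), 2/662 = 0.3% (optic nerve disorder), and 100 to 200 tedizolid patients. Both percentages reproduce.

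| Outcome | n = 100 | n = 200 |
|---|---|---|
| Peripheral neuropathy, n × 1.2% | 1.2 | 2.4 |
| Optic nerve disorder, n × 0.3% | 0.3 | 0.6 |

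One carried-over neuropathy case equals 1/2.4 = 42% to 1/1.2 = 83% of the expected count. It adds 1/200 = 0.5 to 1/100 = 1.0 percentage points to a rate expected to be 1.2%. For optic nerve disorder, one case exceeds the whole expected count.

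**3. How many carried-over cases?**

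The protocol does not give this, so the following is an assumed range. Let q be the share of patients with a retained prior code, and f the share of those with a first qualifying drug or test in follow-up.

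- False events = n × q × f
- Observed neuropathy risk = 0.012 × (1 − q) + q × f

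Low end, q = 0.5%, f = 25%, n = 100: 0.125 false events. Observed risk is 0.01194 + 0.00125 = 0.01319, of which 9% is false.

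High end, q = 2%, f = 100%, n = 200: 4 false events. Observed risk is 0.01176 + 0.02 = 0.03176, of which 63% is false.

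**4. What the feasibility zero allows**

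If the zero rests on 62 tedizolid users (an assumption; 62 is the denominator of the injection figure in section 7.2.5), the one-sided 95% upper bound is 1 − 0.05^(1/62) = 4.7%. That is 4.7 patients at n = 100 and 9.4 at n = 200. The zero points to few such patients but does not exclude a number above the true event count. It gives no information on linezolid, which section 7.5 assumes to be about ten times larger.

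**5. Does it reach the odds ratio?**

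Sections 7.1 and 7.8.2 estimate an odds ratio only with at least 10 events in each group. The high end above gives about 2.4 + 4 = 6.4 tedizolid neuropathy events. Pooling both outcomes gives 1.5% × 200 + 4 = 7. Without any carry-over, the chance of 10 or more at n = 200 and 1.2% is about 0.0002. Only the extreme corner (q = 4.7%, f = 100%, n = 200) passes the threshold: 200 × 0.0584 = 11.7.

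**The case against.** The strongest reply is the feasibility result. No tedizolid first user had a code in 90 days, a window that covers the 60-day lookback, and these are the very patients at issue. If the stricter screen would cost almost nobody, almost nobody leaks through the current one. For tedizolid this largely stands and keeps the expected size small. It does not close the point, because the count is small, its denominator is not stated, and linezolid is not covered. The 62 used above is borrowed: the 72.7% in section 7.2.3 is not a fraction of 62 (45/62 = 72.6%), so the 4.7% bound is only indicative.

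Further, a retained patient is not a false event. The patient must also have no qualifying care in the lookback and then a first one within the roughly 30 days of follow-up assumed in section 7.5. That is correct, and it is why f appears in the working.

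Three stronger conclusions are tempting, and the protocol does not support them.

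- *A reader might infer that carried-over cases would decide the comparison between drugs.* The 10-event condition makes that unlikely on the plan's own numbers. The same exclusion also applies to both groups, and nothing in the text shows that leakage would differ between them.
- *A reader might infer that sensitivity analysis 8 keeps the two-condition screen while counting code-only events.* The text is silent. Because it redefines the disorders themselves, carrying the new definition into exclusion 3 is an equally natural reading. It is ambiguous, not shown to be wrong.
- *A reader might infer that the index date is a further source of false events,* since it lies outside both lookback and follow-up. A first event dated that day precedes follow-up and is not counted on treatment. At most, a patient remains in the denominator.

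Section 7.10 already says that the outcome algorithms may lack optimal sensitivity and specificity. That discloses imperfect event counting. It does not address using the same rule as the entry screen.

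**Conclusion.** The point holds as a defect of the entry screen. Followed literally, exclusion 3 and sensitivity analysis 6 retain patients with a confirmed prior code but no qualifying drug, test or procedure, and section 7.3.2 can then count that prior disease as a new event. This rests on the text alone.

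The size is unknown. Under the assumed ranges it is 0.1 to 4 false tedizolid neuropathy events, against 1.2 to 2.4 expected true ones. The feasibility zero favours the low end for tedizolid and is silent on linezolid. What is exposed is the descriptive rate in each group, which is likely to be the study's main output. The change should be made because it is cheap and removes an avoidable bias, not because a large effect has been shown.

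**What to change.** 1. **Section 7.2.3, exclusion 3.** Exclude patients with any confirmed diagnosis code of peripheral neuropathy or optic nerve disorder recorded in the lookback period, whether or not a drug, procedure or test accompanies it. Confirmed codes suffice, since the outcome uses confirmed codes only. Keep a single exclusion covering both disorders, so that there is one cohort.
2. **Section 7.8.3 (6).** Apply the same code-only rule over 365 days.
3. **Section 7.8.3 (8).** State that the code-only exclusion applies here too, using the recorded diagnosis date and not the assigned month-end date. Otherwise a code entered in the index month before the index date would be dated on or after it and escape the screen.
4. **Month-level dates.** Where only the diagnosis month is known, screen on months before the index month. A code in the index month cannot then be placed before or after treatment start, and excluding on it could remove true on-treatment events.
5. **Section 7.3.2.** Keep the two-condition definition for counting events.

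The cost is a sentence in 7.2.3 and matching wording in 7.8.3 (6) and (8). A few patients may be lost, probably close to none in the tedizolid group on the feasibility count. The linezolid loss is unknown. Where dates are month-level, some pre-index codes from the index month will still get through.

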7.2.5 Longitudinality

This is a longitudinal surveillance. Factors to be considered in describing the clinical course of each patient are as follows:

1. All patients must have 60 days history before the index date (Lookback period).
2. The treatment period (continuous prescription period) for the tedizolid and linezolid groups is defined as from the index date to the end date of the last prescription period + grace period - 1.

A prescription period will be defined as prescription date + number of day's supply - 1.

| | |
|---|--|
| PRODUCT: MK-1986 | PROTOCOL/AMENDMENT VERSION NO.: 1986-047-00-V3 |
| REVOPS ID NO: NIS106696 EPIDEMIOLOGY NO.(PE STUDIES ONLY): EP08063.004 | NIR DRC APPROVAL DATE: NOVEMBER 25, 2025 |

The gap period is defined as the period from the end of the prescription period to the start of the next prescription period.

If the gap period is <14 days, the prescription periods are considered to be continued, and the prescription periods are consolidated. If the gap period is ≥ 14 days, the prescription periods are not consolidated, and the prescription periods after the gap period are not included in the analysis.

The gap periods for primary analysis are set at 14 days for tedizolid and linezolid based on the results of the feasibility study. It showed that the median gap period in the 1st use was [redacted] days for tedizolid group and [redacted] days for linezolid group. However, an analysis with a gap period of 7 days was also conducted as a sensitivity analysis (see Section 7.8.3 (3)). In addition, the feasibility study showed that the percentage of injections used was quite high (55/62 (88.7%) for tedizolid group and 476/574(82.9%) for linezolid group). Since most of the medication was injectable, the possibility of residual medication was considered to be low, and unnecessary to set a gap period longer than 14 days. In this study, this definition will be used as a common definition for tablets and injections. Also, it was considered unnecessary to set different treatment periods for injectable and oral agents.

The grace period is defined as the duration during which the effects of the drug may still be present, considering residual medication. It is considered the period that is added to the end date of the last prescription period. In this study, the grace period is set to be the same length as the gap period.

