7.3 Variables

7.3.1 Exposure

The group of patients who are newly prescribed/exposed to tedizolid during the cohort entry period (21-Aug-2018 to 31-Mar-2025) will be considered as the tedizolid group. The start date of the cohort entry period coincides with the date tedizolid was placed on the market, so the index date corresponds to the new incident use of tedizolid in the database. The group of patients who newly start linezolid during the cohort entry period (21-Aug-2018 to 31-Mar-2025) will be considered as the linezolid group.

Patients will be considered as being exposed to the medication if there is a record for drug supply, i.e., prescription or dispensation record. Each prescription or dispensation will initiate a new prescription period that ends after the drug supply runs out. Also, a gap day between two prescription / dispensation records will be considered as a continuous prescription period if it is below the gap period.

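### Exclusion 4 is stated on prescription record dates while exposure is defined by days' supply, so a multi-day course supplied once on the index date is excluded and eligibility hangs on a later record

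*Protocol*

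**What the plan says.** Section 7.2.3, criterion 4, excludes "Patients who have prescription records for tedizolid or linezolid only on the index date". It does not mention days' supply, sets no window for a later record, and gives no reason.

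The index date is tied to records: "Index date is the first prescription date of tedizolid or linezolid observed in the cohort entry period", taken from SS-MIX2 prescription orders (Section 7.2.2).

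Exposure is tied to supply. Section 7.2.5: "A prescription period will be defined as prescription date + number of day's supply - 1". Section 7.3.1: "Each prescription or dispensation will initiate a new prescription period that ends after the drug supply runs out".

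Prescription periods separated by less than 14 days are joined. Where the gap is 14 days or more, "the prescription periods after the gap period are not included in the analysis". A grace period is then added: "In this study, the grace period is set to be the same length as the gap period", so 14 days in the primary analysis.

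Section 7.2.4: "The follow-up will begin on the day after the index date".

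On route of administration, Section 7.2.5 reports injection use in the feasibility study as "55/62 (88.7%) for tedizolid group and 476/574(82.9%) for linezolid group". Section 7.2.2 admits outpatients as well as inpatients and emergency cases.

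**The concern.** Elsewhere in the Protocol, one record can represent a full course, because exposure lasts as long as the supply. Exclusion 4 treats that patient as if nothing followed the index date. The two rules can therefore rank patients in the wrong order, dropping a longer exposure and keeping a shorter one.

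The criterion also makes entry depend on something that happens after follow-up has begun. A patient who stops or dies before a second record leaves the cohort, along with that risk time and any event in it. This sits badly with Section 7.1, which chooses the new-user design partly to reduce selection bias.

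The stakes are higher because the tedizolid group is small. Section 7.5 expects 100-200 patients and reports that no scenario examined reaches 80% power. Section 7.2.3 shortens the lookback specifically to gain patients. Dropping validly exposed patients works against that aim.

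**Working it through.** **Inputs.** Gap threshold 14 days, grace period 14 days and the prescription-period formula (Section 7.2.5); follow-up from day 1 (Section 7.2.4); exclusion 4 (Section 7.2.3). The index date is day 0. The record patterns are illustrative and are not taken from the Protocol.

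**Formulas.**
- Last supply day = record day + days' supply − 1.
- Treatment period end = last supply day of the consolidated period + 14 − 1.
- Exclusion 4 read literally: excluded if every record date is day 0.

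**Results.**

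| Records of tedizolid or linezolid | Last supply day analysed | Treatment period end | Exclusion 4 |
|---|---|---|---|
| Day 0, 7 days' supply | 0 + 7 − 1 = 6 | 6 + 13 = day 19 | Excluded |
| Day 0, 10 days' supply | 9 | day 22 | Excluded |
| Day 0, 14 days' supply | 13 | day 26 | Excluded |
| Days 0 and 1, one day each | 1 | day 14 | Kept |
| Day 0, one day | 0 | day 13 | Excluded |
| Days 0 and 40, one day each | 0 (second record lies beyond a gap of 14 days or more) | day 13 | Kept |

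The first three rows apply equally to tablets supplied once and to a multi-day injection entered as a single order.

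The last two rows have the same analysed exposure and the same treatment period, but opposite eligibility. The only difference is a record that the analysis itself discards.

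The criterion names either drug, so a one-day user of tedizolid with a linezolid record on day 1 also escapes it. Under Section 7.2.4 that second record ends follow-up.

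**Whether the rule is needed to secure follow-up.** It is not. With the grace period, even a one-day user has defined risk time from day 1 to day 13.

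**Route of administration.** The stated shares reproduce: 55/62 = 88.7% and 476/574 = 82.9%. The remainders are 62 − 55 = 7, or 7/62 = 11.3%, for tedizolid, and 574 − 476 = 98, or 98/574 = 17.1%, for linezolid. The difference is 5.8 percentage points (Fisher exact p = 0.28).

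**Whether anything offsets the rule.** Exclusions 1 and 3 each have a sensitivity analysis, and exclusion 2 has a stated reason. None of the eight analyses in Section 7.8.3 relaxes exclusion 4, and Section 7.10 does not list it as a limitation.

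**The case against.** **The term is undefined.** Section 7.2.3 does not say what counts as a prescription record. Section 7.2.1 lists administration records among the sources, and Section 7.3.1 refers to dispensation. If administration records count, many inpatient courses would carry several dates and pass. This stands and narrows the problem, but an outpatient course supplied once would still be excluded.

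**The gap rule may already deal with late records.** Section 7.2.5 removes periods after a long gap from the analysis. That governs which exposure is analysed. Exclusion 4 does not refer to it, so eligibility remains open on the wording.

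**The criterion followed a regulatory consultation.** Section 3 shows that it was added in the update made after consultation with the PMDA, and a rationale may exist in papers not shown. That explains where the rule came from, but does not reconcile it with Sections 7.2.5 and 7.3.1.

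**Stronger readings that the Protocol does not support.**
- A reader might multiply the non-injection shares by the planned group sizes and report 11-23 tedizolid and 171-341 linezolid patients wrongly excluded. Those counts cannot be derived: 100-200 is already net of exclusions, single-supply counts are not given, and the patients outside the injection count are not shown to have used tablets only.
- A reader might infer that oral users bear most of the loss. That needs injections to be recorded day by day, which the Protocol does not state.
- A reader might infer a known bias between groups. The shares differ only modestly, single-supply rates by group are unknown, and the same rule applies to both.
- A reader might call this immortal time. It is selection on post-index prescribing. An early event does not prevent a later record, so such a patient can still enter and be counted; those lost are the ones who stop or die first. If records are daily, that interval is about one day.

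**Conclusion.** The point holds as a conflict between a stated eligibility rule and the Protocol's own definition of exposure. As written, exclusion 4 removes patients whose treatment period runs 19 to 26 days past index in the examples, and keeps patients whose period ends on day 13 or 14. It also makes entry depend on a record after follow-up has started.

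This goes beyond wording, because it decides who enters a very small group and nothing in the plan tests its effect. The number affected could be close to zero or material, and the Protocol does not allow it to be estimated. Nor can the direction of any between-group bias be fixed. The shares of 11.3% and 17.1% show only that use not counted as injection is not negligible.

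The conclusion rests on a literal reading of the criterion, on a 14-day gap and grace period, and on single-date multi-day supplies occurring in the data. The last is plausible, since outpatients are eligible, but it is not quantified.

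**What to change.** Restate exclusion 4 on exposure: exclude patients whose first consolidated prescription period of the index drug, computed from days' supply under Section 7.2.5 and taken before the grace period is added, ends on the index date. The condition must be applied before the grace period, because afterwards every period reaches at least day 13. This keeps multi-day supplies recorded once. It also prevents a record after a gap of 14 days or more, or a record of the other drug, from qualifying a one-day user.

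Define in the same place which records count: order, dispensation or administration.

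Add to Section 7.8.3 a sensitivity analysis without exclusion 4. The restatement alone does not remove the dependence on later prescribing, because a course recorded day by day would still need a post-index record to qualify.

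The cost is one sentence, a small derivation change using a variable already required, and one extra analysis. The regulator should be notified, because the criterion entered in the update that followed its consultation.
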